### 6.6.1 Management of Infections

Subjects with evidence of existing infection should be closely monitored while being treated with AMG 397. Subjects with active systemic infections requiring IV antibiotics, antivirals, or antifungals should not be dosed with AMG 397 until infection per exclusion criteria in [Section 4.2](#). Management should be tailored to the appropriate prophylaxis and/or treatment for the underlying infection according to the local standard of care and institutional guidelines.

Subjects who may experience neutropenia are at a high risk for infectious complications. As appropriate, these subjects should be administered prophylactic antibacterial (treatment with ciprofloxacin) and antifungal (treatment with posaconazole).

These subjects should be monitored for early signs of breakthrough infections after the initiation of antibacterial therapy to prompt additional evaluation and possible therapy modification. Subjects experiencing diarrhea should be closely monitored for their electrolyte levels.

### 6.6.2 Management of Renal Toxicities

Renal dysfunction is one of the multiple myeloma-related organ/tissue dysfunction. Renal function must be monitored closely during treatment with AMG 397. Serum chemistry values, including BUN, serum creatinine, and urine for urinalysis and microscopic exam (microscopic exam only needed for positive dipstick), must be obtained per the schedule of assessments (see [Table 4](#)). Management should be tailored to the appropriate treatment for the underlying renal disorder according to the local standard of care and institutional guidelines.

### 6.7 Hepatotoxicity Stopping and Rechallenge Rules

Subjects with abnormal hepatic laboratory values (eg, alkaline phosphatase [ALP], aspartate aminotransferase [AST], alanine aminotransferase [ALT], total bilirubin [TBIL] or international normalized ratio [INR]) or signs/symptoms of hepatitis may meet the criteria for withholding of investigational product. Withholding is either permanent or conditional depending upon the clinical circumstances discussed below (as specified in the FDA Guidance for Industry Drug-Induced Liver Injury: Premarketing Clinical Evaluation, July 2009).

#### 6.7.1 Criteria for Permanent Withholding of AMG 397 due to Potential Hepatotoxicity

AMG 397 should be permanently withheld and the subject should be followed according to the recommendations in [Appendix A](#) (Additional Safety Assessment Information) for possible drug-induced liver injury (DILI), if ALL of the criteria below are met:

- Increased AST or ALT from the relevant baseline value as specified below:

Baseline AST or ALT value	AST or ALT elevation
< ULN	> 3x ULN

AND

- TBIL > 2x upper limit of normal (ULN) or INR > 1.5

AND

- No other cause for the combination of the above laboratory abnormalities is immediately apparent; important alternative causes for elevated AST/ALT and/or elevated TBIL values include, but are not limited to:
  - Hepatobiliary tract disease
  - Viral hepatitis (eg, Hepatitis A/B/C/D/E, Epstein-Barr Virus, Cytomegalovirus, Herpes Simplex Virus, Varicella, Toxoplasmosis, and Parvovirus)
  - Right sided heart failure, hypotension or any cause of hypoxia to the liver causing ischemia
  - Exposure to hepatotoxic agents/drugs including herbal and dietary supplements, plants, and mushrooms,
  - Heritable disorders causing impaired glucuronidation (eg, Gilbert's syndrome, Crigler-Najjar syndrome) and drugs that inhibit bilirubin glucuronidation (eg, indinavir, atazanavir)
  - Alpha-one antitrypsin deficiency
  - Alcoholic hepatitis
  - Autoimmune hepatitis
  - Wilson's disease and hemochromatosis
  - Nonalcoholic Fatty Liver Disease including Steatohepatitis (NASH)
  - Non-hepatic causes (eg, rhabdomyolysis, hemolysis)

#### 6.7.2 Criteria for Conditional Withholding of AMG 397 due to Potential Hepatotoxicity

For subjects who do not meet the criteria for permanent discontinuation of AMG 397 outlined above and have no underlying liver disease and eligibility criteria requiring normal transaminases and TBIL at baseline or subjects with underlying liver disease and baseline abnormal transaminases, the following rules are recommended for withholding of Amgen investigational product and other protocol-required therapies:

Elevation of either AST or ALT according to the following schedule:

Baseline AST or ALT value	AST or ALT elevation
Any	> 8x ULN at any time
Any	> 5x ULN but < 8x ULN for $\geq 2$ weeks
Any	> 5x ULN but < 8x ULN and unable to adhere to enhanced monitoring schedule
Any	> 3x ULN with clinical signs or symptoms that are consistent with hepatitis (such as right upper quadrant pain/tenderness, fever, nausea, vomiting, jaundice).

- OR: TBIL > 3x ULN at any time
- OR: ALP > 8x ULN at any time

AMG 397 should be withheld pending investigation into alternative causes of DILI. If investigational product(s) is withheld, the subject should be followed according to recommendations in [Appendix A](#) for possible DILI. Rechallenge may be considered if an alternative cause for impaired liver tests (ALT, AST, ALP) and/or elevated TBIL, is discovered and the laboratory abnormalities resolve to normal or baseline.

### **6.7.3 Criteria for Rechallenge of AMG 397 After Potential Hepatotoxicity**

The decision to rechallenge the subject should be discussed and agreed upon unanimously by the subject, Principal Investigator, and Amgen.

If signs or symptoms recur with rechallenge, then AMG 397 should be permanently discontinued. Subjects who clearly meet the criteria for permanent discontinuation (as described in [Section 6.2.1.3](#)) should not be rechallenged. If signs or symptoms recur with rechallenge, then AMG 397 should be permanently discontinued.

### **6.8 Concomitant Therapy**

Throughout the study, Investigators may prescribe any concomitant medications or treatments deemed necessary to provide adequate supportive care except for those listed in [Section 6.10](#)

Concomitant therapies are to be collected from screening start through the EOS visit. All concomitant medication will be recorded on the eCRF including all prescription, over-the-counter, herbal supplements, and IV medications, transfusions and fluids.

Subjects should receive full supportive care during the study, including transfusions of blood and blood products, and treatment with antibiotics, anti-emetics, anti-diarrheals, and analgesics, G-CSF and other care as deemed appropriate, and in accordance with their institutional guidelines. For subjects with AML hydroxyurea for 7 days at a dose of 1 – 10 g/day is allowed prior to the first cycle of AMG 397 treatment for subjects with high WBC (> 25,000 cells/ul) and during the first cycle but not on dosing days at a dose of up to 5 g/day.

For all concomitant medication collect therapy name, indication, dose, unit, frequency, route, start date, and stop date.

### **6.9 Product Complaints**

A product complaint is any written, electronic or oral communication that alleges deficiencies related to the identity, quality, durability, reliability, safety, effectiveness, or performance of a drug(s) or device(s) after it is released for distribution to market or

clinic by either Amgen or by distributors and partners for whom Amgen manufactures the material.

This includes any drug(s), device(s), or combination product(s) provisioned and/or repackaged /modified by Amgen. Drug(s) or device(s) includes investigational product.

Any product complaint(s) associated with an investigational product(s) or non-investigational product(s) or device(s) supplied by Amgen are to be reported according to the instructions provided in the IPIM.

## **6.10 Excluded Treatments and Procedures During Study Period**

The following medications and/or therapies should not be administered during the study:

- Allogeneic stem cell transplant
- Autologous stem cell transplant
- Antitumor therapy (chemotherapy, antibody therapy, molecular-targeted therapy, retinoid therapy, or investigational agent or procedures)
- Systemic or focal radiotherapy
- Over-the-counter medication(s) that was not reviewed and approved by the principal investigator and the Amgen medical monitor
- Any known inhibitors of P-gp or grapefruit juice or grapefruit containing products that were not reviewed and approved by the principal investigator and the Amgen medical monitor
- Herbal medicines (eg, St. John's wort), vitamins, and supplements that were not reviewed and approved by the principal investigator and the Amgen medical monitor
- Any known cytochrome P450 (CYP) 3A4 sensitive substrates, with a narrow therapeutic window, that were not reviewed and approved by the principal investigator and the Amgen medical monitor

If use of any other prior or concomitant medication or procedure is in question, please refer to prescribing information and/or consult with Amgen Medical Team.

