217. Males who are unwilling to abstain from sperm donation while on study through 3 months after receiving the last dose of study drug.
218. History or evidence of any other clinically significant disorder, condition or disease that, in the opinion of the investigator or Amgen physician, if consulted, would pose a risk to subject safety or interfere with the study evaluation, procedures or completion.
219. Use of any over-the-counter or prescription medications within 14 days or 5 half-lives (whichever is longer), prior to study day 1 that was not reviewed and approved by the principal investigator and the Amgen medical monitor
220. Use of herbal medicines (eg, St. John's wort), vitamins, and supplements consumed by the subject within 14 days prior to study day 1 that was not reviewed and approved by the principal investigator and the Amgen medical monitor
221. Use of any known inhibitors of P-gp within 14 days or 5 half-lives (whichever is longer) or grapefruit juice or grapefruit containing products within 7 days prior to study day 1 that was not reviewed and approved by the principal investigator and the Amgen medical monitor
222. Use of known cytochrome P450 (CYP) 3A4 sensitive substrates, (**with a narrow therapeutic window**), within 14 days or 5 half-lives (whichever is longer) of the drug or its major active metabolite, whichever is longer, prior to study day 1 that was not reviewed and approved by the principal investigator and the Amgen medical monitor

Approved

223. Use of known P-gp substrates (**with a narrow therapeutic window**) within 14 days or 5 half-lives (whichever is longer) prior to study day 1 that was not reviewed and approved by the principal investigator and the Amgen medical monitor
224. Subject likely to not be available to complete all protocol-required study visits or procedures, and/or to comply with all required study procedures (eg, long term follow-up) to the best of the subject and investigator's knowledge
225. Known sensitivity to any of the products or component to be administered during dosing

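### Narrow-window P-gp substrates need approval before day 1 (exclusion 223), but Section 6.10 has no matching line once AMG 397 dosing starts

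*Protocol*

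**What the plan says.** **The risk.** Protocol Section 2.2.3 and the drug-interaction paragraph of Section 2.2.4 conclude from physiologically based modelling that AMG 397 may interact with CYP3A4 and P-gp. Section 2.2.4 considers an interaction through other CYPs and transporters unlikely. It also notes that AMG 397 is itself a P-gp substrate.

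**Entry.** Exclusions 219 to 223 in Section 4.2 each bar certain co-medication before study day 1 unless the investigator and the medical monitor have approved it. Criterion 219 is the general one: "Use of any over-the-counter or prescription medications within 14 days or 5 half-lives (whichever is longer), prior to study day 1". Criterion 222 covers CYP3A4 sensitive substrates with a narrow therapeutic window. Criterion 223 covers P-gp substrates with a narrow therapeutic window ("Use of known P-gp substrates"), over a window of 14 days or 5 half-lives.

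**On study.** Section 6.8 lets investigators prescribe whatever supportive care needs, apart from what 6.10 lists. The relevant 6.10 lines are:

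- "Antitumor therapy (chemotherapy, antibody therapy, molecular-targeted therapy, retinoid therapy, or investigational agent or procedures"
- over-the-counter products that lack the same two-party approval
- "Any known inhibitors of P-gp or grapefruit juice or grapefruit containing products that were not reviewed and approved"
- unapproved herbal medicines, vitamins and supplements
- "Any known cytochrome P450 (CYP) 3A4 sensitive substrates, with a narrow therapeutic window, that were not reviewed and approved"

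Section 6.10 closes with a consult clause: "If use of any other prior or concomitant medication or procedure is in question, please refer to prescribing information". It also offers consultation with the sponsor's medical team.

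**Risk guidance.** Section 6.5.4 says that subjects receiving drugs named in the exclusion criteria or on the prohibited list will be kept out of the study. It then asks for caution when AMG 397 is given with narrow-window drugs whose labels warn about CYP3A4 and P-gp inhibitors.

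**The concern.** AMG 397 can raise exposure to a P-gp substrate only once AMG 397 is being given. The explicit approval step for this class covers only the period before that. The parallel CYP3A4 class has the approval step both before day 1 and during treatment, and the protocol gives no reason for treating the two differently.

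The P-gp line that 6.10 does carry does not fill the gap. It concerns P-gp inhibitors, which act on AMG 397 as a substrate. Criterion 223 looks the other way, at the effect of AMG 397 on another drug with little margin for a rise in level.

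What is at stake is patient safety in a first-in-human study. Section 6.8 itself expects antibiotics, anti-emetics, anti-diarrheals and analgesics during treatment, so new prescriptions after day 1 are part of the plan.

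**Working it through.** No formula applies; the check is a side-by-side reading of Sections 4.2, 6.10, 6.8 and 6.5.4.

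**Step 1. Match each approval-based entry criterion to 6.10.**

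| Entry criterion (4.2) | Subject matter | On-study line in 6.10 |
|---|---|---|
| 219 | Over-the-counter or prescription drugs | Over-the-counter part only |
| 220 | Herbals, vitamins, supplements | Yes |
| 221 | P-gp inhibitors, grapefruit | Yes |
| 222 | Narrow-window CYP3A4 sensitive substrates | Yes |
| 223 | Narrow-window P-gp substrates | None |

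Three of the five are carried in full, one in part, and one not at all: 3 + 1 + 1 = 5. Before day 1 a prescription narrow-window P-gp substrate meets two approval rules, 219 and 223. During dosing neither rule has a line that reaches it as such.

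**Step 2. Take out what other 6.10 lines already catch.** Section 6.10 has eight bullets. Three are procedures (two kinds of transplant, and radiotherapy). The other five can each catch some P-gp substrates: those that are antitumor therapy, over-the-counter products, P-gp inhibitors, herbals or supplements, or narrow-window CYP3A4 sensitive substrates. The gap is what remains: a prescription narrow-window P-gp substrate in none of these groups, started or restarted after day 1.

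**Step 3. See what governs the remainder.**

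- Section 6.8 makes permission the default for supportive care, so absence from 6.10 means the drug is allowed.
- Section 6.5.4 asks for caution, not approval.
- The closing clause of 6.10 applies only where there is doubt. It offers prescribing information as an alternative to consulting the sponsor, and it requires no approval.
- Recording on the eCRF (6.8) and review of concomitant medication at dose-level meetings (6.2.1.2) both come after the drug has been given.

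**Step 4. Compare with the CYP3A4 class.** The same caution and the same consult clause also apply to narrow-window CYP3A4 substrates, yet the sponsor gave that class its own approval line as well. By the protocol's own standard the two weaker provisions were not enough for the parallel risk.

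**The case against.** **On-study handling exists.** The 6.5.4 caution addresses much the same drugs during treatment, and the 6.10 consult clause adds a second prompt. A sponsor may reasonably choose caution over approval for one subclass. This stands in part: the class is not ignored, and the documents do not show whether the omission was intended. It does not explain why the CYP3A4 class needed more.

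**The sponsor deliberately narrowed 6.10.** The Amendment 1 change log shows prescription drugs being removed from the general on-study line. That is a choice to respect, and nothing here asks to reverse it. Narrowing a general rule is different from leaving one of two named interaction classes without a specific rule.

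**The text may be superseded.** SAP Section 1 works from protocol amendment 4, dated 09 December 2020, and SAP Section 3.1 describes a redesign to low weekly doses with the original Part 1 closed to enrollment. This stands fully. Amendment 4 was not supplied, so the point is about the supplied version only.

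**A reader might infer that 6.5.4 contradicts 6.8**, by taking its exclusion sentence as an on-study bar. The documents do not support that. Criterion 223 is timed before day 1, and the caution sentence that follows presupposes co-administration. The coherent reading is that the exclusion sentence governs entry and the caution governs treatment.

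**A reader might also equate the time AMG 397 stays in the body with time at risk.** That is not supported either. Section 2.2.3 gives a P-gp IC50 of 8.7 µM, and Table 2 predicts a Cmax of 2.79 µg/mL at 640 mg and 0.35 µg/mL at 80 mg. The molecular weight at which peak equals IC50 is Cmax / IC50: 2.79 mg/L ÷ 8.7 µmol/L ≈ 321 g/mol at 640 mg, and 0.35 ÷ 8.7 ≈ 40 g/mol at 80 mg. The documents do not give the molecular weight. For any value above these, even the total peak is below the IC50, and Section 2.2.3 puts the unbound fraction at only 0.0048 to 0.027. This does not overturn the modelled P-gp potential, and gut concentrations may be higher. It does mean that hours of drug presence are not hours of inhibition.

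**Conclusion.** The point holds for the supplied protocol. Criterion 223 is the only one of the five approval-based co-medication criteria with no on-study counterpart. As a result, a prescription narrow-window P-gp substrate outside the other 6.10 lines can be started during dosing with a caution and a conditional consult clause, and no prior approval.

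The size is modest. The residual class is narrow, the documents name no drug in it, and the number of subjects affected cannot be derived. No endpoint, dose-escalation rule or analysis changes. It would be too strong to say that the protocol leaves P-gp substrates unaddressed during treatment, because 6.5.4 and the end of 6.10 do reach them.

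The conclusion rests on two assumptions: that 6.8 means what it says in making 6.10 the list of exceptions, and that the exclusion sentence in 6.5.4 is an entry rule. The change is worth making because it closes a safety gap at almost no cost. Confidence is medium, mainly because amendment 4 was not available.

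**What to change.** First check whether protocol amendment 4 already contains the line. If not, add one bullet to Section 6.10 with the same form and approval clause as the CYP3A4 bullet, naming known P-gp substrates with a narrow therapeutic window; criterion 223 already supplies the terms. The bullet bars nothing outright. It asks for review by the investigator and the medical monitor before such a drug is started on study.

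Optionally, add a phrase to Section 6.5.4 saying that its exclusion sentence applies at entry.

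The cost is one line of text and occasional approval requests to the medical monitor during treatment. A general approval rule for on-study prescription drugs is not needed.

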## **7. STUDY PROCEDURES**

### **7.1 Schedule of Assessments**

Please refer to [Table 4](#) for Schedule of Assessments.

Once lead-in dosing is initiated follow [Table 5](#) for Cycle 1 only. For all subsequent cycles and study periods follow [Table 4](#).

**Table 4. Schedule of Assessments**

CYCLE(S)	SCREENING	TREATMENT																								EOT	SAFETY FOLLOW-UP	LTFU (26)					
		1												2					3			Every cycle from 3 & beyond											
		1												2					3	1	2	3	1										
WEEK(S)	DAY(S)	-21	-1	1								2								3	4	8					15	22	1	8	15	1	
DAY(S)	Pre-dose	0	1	2	3	5	8	12	Pre-dose	0	1	2	3	5	8	12	24h after D2 dose	48h after D2 dose	Pre	0	2	3	5	Pre-dose unless specified									
HR(S) (relative to time of dosing)																																	
Survival/Subsequent anti-cancer therapy (6)																																	
LAB ASSESSMENTS																																	
AMG 397 PK (7)		X		X	X	X	X	X	X	X	X	X	X	X	X	X	X	X	X	X	X	X	X	X	X	X	X	X	X				
CBC with diff (8)	X	X	X						X							X	X	X						X	X	X	X	X	X				
Chemistry (9)	X	X	X			X		X	X	X			X		X	X	X	X						X	X	X	X	X	X				
Coagulation	X	X	X						X						X	X	X						X	X	X	X	X	X	X				
Pregnancy test (10)	X	X																								X		X	X				
Urine sample collection (11)	X	X					X	X						X					X				X				X		X				
Hepatitis serology, HIV	X																																

Footnotes are defined at the end of [Table 5](#)

Approved

Table 4. Schedule of Assessments

CYCLE(S)	SCREENING	TREATMENT																		EOT	SAFETY FOLLOW-UP	LTFU (26)																
		1												2			Every cycle from 3 & beyond																					
WEEK(S)		1												2			3		1	2	3	1																
DAY(S)	-21 to -2	-1	1						2						3	4	8			15	22	1	8	15	1													
HOURL(S) (relative to time of dosing)			Pre-dose	0	1	2	3	5	8	12	Pre-dose	0	1	2	3	5	8	12	24h after D2 dose	48h after D2 dose	Pre	0	2	3	5	Pre-dose unless specified												
BIOMARKER and DISEASE ASSESSMENTS																																						
Bone marrow aspirate (12)	X																																					
Whole blood Na/Hep (13)		X				X	X				X																											
Whole blood Cytochex (14)		X									X								X	X	X																	
Plasma	X																																					
Serum	X																																					
Cell Pellet	X																																					
MM SUBJECTS ONLY																																						
SPEP/UPEP/Immunofixation (15)	X																																		X		X	X
SFLC (16)	X																																		X		X	X
Beta-2 microglobulin	X																																					X
Quantitative Ig (17)	X																																					X

Approved

Footnotes are defined at the end of [Table 5](#)

Table 4. Schedule of Assessments

CYCLE(S)	SCREENING	TREATMENT																									EOT	SAFETY FOLLOW-UP	LTFU (26)			
		1										2					3			Every cycle from 3 & beyond												
WEEK(S)		1										2					3			1												
DAY(S)	-21 to -2	-1	1					2					3	4	8			15	22	1	8	15	1									
HOURL(S) (relative to time of dosing)		Pre-dose	0	1	2	3	5	8	12	Pre-dose	0	1	2	3	5	8	12	24h after D2 dose	48h after D2 dose	Pre	0	2	3	5	Pre-dose unless specified							
Bone marrow biopsy	X																															
Bone marrow aspirate (18)		----- Repeat collection in case of CR -----																														
Plasmacytoma (19)	X																															
Skeletal survey (20)	X																															
NHL SUBJECTS ONLY																																
Lymph Node Biopsy	X																															
Whole blood plasma (Dose expansion only) (21)	X																											X			X (21)	X
Bone marrow biopsy (22)	X																															
PET-CT and CECT Imaging (23)	X																											X			X (23)	X
MRI Brain (24)	X																															
AML SUBJECTS ONLY																																
Bone marrow aspirate (25)																												X			X (25)	X

Approved

Footnotes are defined at the end of [Table 5](#)

**Table 5. Schedule of Assessments (Cycle 1 ONLY After Lead-in Dosing is Implemented)**

CYCLE	CYCLE 1 ONLY																																					
	-21 to -2	-1	1						2						3	4	7	8						9						10	11	15	22					
HOUR(S) (relative to time of dosing)		Pre-dose	0	1	2	3	5	8	12	Pre-dose	0	1	2	3	5	8	12	24h after D2 dose	48h after D2 dose	Pre-dose	0	1	2	3	5	8	12	Pre-dose	0	1	2	3	5	8	12	24h after D9 dose	48h after D9 dose	
Informed consent	X																																					
Clinical evaluation (1)	X	X	X							X								X	X	X	X							X							X	X	X	X
Vital signs (T, BP, HR, RR)	X	X	X			X	X	X	X	X			X	X	X	X	X	X	X	X			X	X	X	X	X	X			X	X	X	X	X	X	X	X
12-lead ECG (2)	X	X	X (2)	X	X	X	X	X	X	X	X	X	X	X	X	X	X	X	X	X		X	X	X	X	X	X	X	X	X	X	X	X	X	X	X	X	
Echocardiogram or MUGA	X																																					
Hospitalization (3)		←-----→													←-----→																							
TLS prophylaxis (4)	X																			X																		
AMG 397 dosing (5)			X							X											X						X									X (5)		
Dosing diary review (5)									X										X														X		X	X		
AE Reporting		←-----→																																				
SAE Reporting		←-----→																																				
Prior /concomitant medication(s)		←-----→																																				

Approved

Footnotes are defined at the end of [Table 5](#)

